3.3.2 Safety Endpoint Success Criteria

An observed rate of 17.5% or lower for the proportion of AXIOS patients with AXIOS™ stent related or WON drainage procedure related serious adverse events is required for success.

This rate is similar to the point estimate of the random-effect meta-analysis of AXIOS stent related or WON drainage related serious adverse events for plastic stents provided in Table 2. Note that in the recent systematic review and meta-analysis [10] (Appendix I in Section 21 of the protocol) the complication rates that showed statistically significant differences between plastic stents and LAMS for drainage of WONs were bleeding and stent occlusion, both in favor of LAMS. These findings are particularly important given that (a) bleeding is the most commonly reported serious adverse event, and (b) stent occlusion almost always requires reintervention. It should also be noted that of the plastic stent WON drainage references provided above, even the one reporting the highest complication rates, namely Smoczynski et al [4] conclude that the benefits outweigh the risks: *“In a large group of selected patients with symptomatic walled-off necrosis, endoscopic drainage enables high success rate with acceptable complication rate and low procedure-related mortality.”* Thus, the proposed success criteria for safety seems reasonable and acceptable.

4. GENERAL STATISTICAL METHODS

4.1 Description of Statistical Methods

Descriptive statistics will be presented for all intent to treat (ITT) and treated patients. If the treated and per-protocol (PP) cohorts are different, the primary effectiveness and safety endpoints will also be assessed for the PP cohort. The mean (\pm standard deviation) will be used to describe continuous variables with a normal distribution and the median (and interquartile range) will be used to describe continuous variables with a skewed distribution. Frequency tables will be used to summarize discrete variables. Proportions of patients with adverse events and SAEs will be reported. No hypothesis testing will be performed.

4.2 Analysis Sets

Enrolled Cohort - A subject will be considered enrolled when the ICF is signed.

Intent-to-treat Cohort - The ITT cohort is defined as all subjects who signed the ICF, were evaluated for inclusion/exclusion criteria, and in whom the endoscopic procedure was initiated.

Treated Cohort - The treated cohort is defined as all ITT subjects who have an AXIOS™ stent implanted for the purpose of WON drainage. Subjects in the treated cohort will be counted towards the enrollment ceiling and this cohort will be considered the primary analysis cohort.

Per Protocol Cohort - The PP cohort is defined as all treated subjects for whom an AXIOS™ stent was implanted for the purpose of WON drainage and met all eligibility criteria.

4.3 Control of Systematic Error/Bias

All subjects who have met the inclusion/exclusion criteria and have signed the ICF will be eligible for enrollment in the study. Visual and/or electronic data review will be performed to identify possible data discrepancies. Manual and/or automatic queries will be created in the EDC system and will be issued to the site for appropriate response. Site staff will be responsible for resolving all queries in the database.

4.4 Number of Subjects per Investigative Site

There will be no limit to the number of subjects enrolled at each investigative site.

5. ADDITIONAL DATA ANALYSES

5.1 Additional Endpoints

1. Reduction of WON-related clinical symptoms. *Note: WON-related symptoms as defined in Inclusion Criteria #4 of the protocol.*
2. Technical AXIOS™ stent placement success, defined as placement in desired location using endoscopic/EUS techniques per standard of practice.
3. Technical AXIOS™ stent removal success, defined as ability to remove the AXIOS™ stent using an endoscopic snare or forceps or graspers without AXIOS™ stent removal related serious adverse events.
4. Drainage procedural time: Time elapsed between initial puncture of the WON with electrocautery to endoscope retrieval.
5. Resolution of WON with or without necrosectomy by 6 months post AXIOS™ stent removal.
6. Time to WON resolution using same definition as for primary endpoint, namely:
 - Resolution of WON with endoscopic drainage defined as radiographic decrease of WON size to ≤ 3 cm evaluated by CT scan or MRI.
7. Recurrence of WON after initial resolution and up to 6 months post AXIOS™ stent removal.
8. Stent lumen patency, evaluated via imaging or direct visual inspection with endoscope, and defined as one or both of the following:
 - Drainage through AXIOS™ stent visualized from the stomach or bowel, and/or
 - Visual confirmation of AXIOS™ stent lumen patency
9. Fluoroscopy (time) per endoscopic procedure.
10. Incidence of new organ failure from drainage procedure to WON resolution.
11. Change in Quality of life score (SF-12 questionnaire) from baseline to stent removal and end of study

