As in the original IDE, #G130264, there is no formal statistical hypothesis for this study. The proportion of AXIOS patients with reduction of WON size to  $\leq 3$ cm within 60 days from AXIOS™ stent placement in the original IDE is 76.7% (23/30) [95% CI (57.7%, 90.0%)] patients. Given that the WONs in the proposed IDE will have an estimated necrotic material content above 30%, namely larger than in IDE #G130264, a slightly lower success rate of 70% is expected in this study. This success rate is within the range of reported WON resolution rates in several recent publications [2-8] representing 448 patients for which a random effects meta-analysis yields a mid-point WON resolution rate of 67.0% [95% CI (60.0%, 73.4%)] for WON drainage with plastic stents (Table 7.1), an established WON drainage method as described in the ASGE guidelines on treatment of pancreatic fluid collections [9].

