#### Data Analysis:

Descriptive statistics will be presented for all ITT and treated subjects. If the treated and PP cohorts are different, the primary effectiveness and safety endpoints will be assessed for the PP cohort. The mean, standard deviation, minimum, and maximum will be used to describe continuous variables; the median (and interquartile range) will be calculated where appropriate. Frequency tables will be used to summarize discrete variables. Proportions of subjects with adverse events and SAEs will be reported.

Interim Analysis:

No formal interim analyses are planned for the purpose of stopping this study early. Informal interim analysis may be conducted for the purpose of submissions of abstracts to major professional meetings.

Subgroup Analysis:

There are no planned subgroup analyses.

Justification of Pooling:

The analyses will be performed using data pooled across institutions and whether patients had a double pigtail plastic stent placed within the Axios stent. An assessment of the poolability of subjects across sites (double pigtail plastic stent groups) for the primary effectiveness and safety endpoints will be made by fitting logistic regression models with site (double pigtail plastic stent) as a factor and the primary effectiveness and safety endpoints as outcomes. Certain baseline variables may also be explored for pooling.

If the P value for the site (double pigtail plastic stent) is  $\geq 0.05$ , it will be concluded that the endpoint is not different across sites (double pigtail plastic stent groups), and the data can be pooled. If the P value for site (double pigtail plastic stent) from the logistic model is  $< 0.05$ , site (double pigtail plastic stent group) differences will be explored.

Multivariable Analyses:

No multivariable analyses are planned for this study.

Changes to Planned Analyses:

Any changes to the planned statistical analyses made prior will be documented in an amended Statistical Analysis Plan. Changes from the planned statistical methods after performing the analysis will be documented in the clinical study report along with a reason for the deviation.

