3.1.1 Hypothesis

As in the original IDE, #G130264, there is no formal statistical hypothesis for this study. The proportion of AXIOS patients with reduction of WON size to ≤ 3 cm within 60 days from AXIOS™ stent placement in the original IDE is 76.7% (23/30) [95% CI (57.7%, 90.0%)] patients. Given that the WONs in the proposed IDE will have an estimated necrotic material content above 30%, namely larger than in IDE #G130264, a slightly lower success rate of 70% is expected in this study. This success rate is within the range of reported WON resolution rates in several recent publications [1-7] representing 448 patients for which a random effects meta-analysis yields a mid-point WON resolution rate of 67.0% [95% CI (60.0%, 73.4%)] for WON

drainage with plastic stents (Table 1), an established WON drainage method as described in the ASGE guidelines on treatment of pancreatic fluid collections [8].

Table 1. Plastic Stent WON Resolution Rates from Recent Publications [1-7]

Study	% Resolution (x/N)	95% Confidence Interval
Bapaye (2017)	73.8% (45/61)	(60.9%, 84.2%)
Gardner et al (2009)	68.9% (31/45)	(53.4%, 81.8%)
Papachristou (2007)	52.8% (28/53)	(38.6%, 66.7%)
Schmidt (2015)	61.7% (50/81)	(50.3%, 72.3%)
Smoczynski (2015)	75.9% (85/112)	(66.9%, 83.5%)
Abu [name] (2017)	75.0% (27/36)	(57.8%, 87.9%)
Varadarajulu (2011)	60.0% (36/60)	(46.5%, 72.4%)
Random-Effects Meta-Analysis	67.0%	(60.0%, 73.4%)

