5.6.2 Post-procedural Information

Post-procedure information will be collected at regularly scheduled follow-up examinations as detailed in the clinical study event schedule and will be summarized using descriptive statistics for continuous variables (e.g., mean, standard deviation, n, minimum, maximum) and frequency tables or proportions for discrete variables. No formal statistical testing will be performed. Data will be summarized as described in Section 4.1.

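### Time to WON resolution has no analysis method of its own, and the general mean/median rule applied to observed times would report it too short

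*SAP*

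**What the plan says.** SAP 5.1 item 6 (also Protocol 4.3) names the endpoint as "Time to WON resolution using same definition as for primary endpoint". The event is therefore a collection of 3 cm or less on CT or MRI. Nothing is said about when the clock starts, when it stops for a patient who does not resolve, or how the times are summarized.

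The rules that could apply are general:
- SAP 4.1 uses mean and SD for normally distributed variables; otherwise "the median (and interquartile range) will be used to describe continuous variables with a skewed distribution".
- SAP 5.6.2 says that post-procedure information "will be summarized using descriptive statistics for continuous variables", with frequency tables for discrete ones.
- Protocol 7.4 gives mean, SD, minimum and maximum, and adds that "the median (and interquartile range) will be calculated where appropriate".

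Neither document mentions Kaplan-Meier, cumulative incidence, censoring, or a value assigned to unresolved patients.

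On how many will resolve, Protocol 7.1 says that "a slightly lower success rate of 70% is expected in this study", and SAP 3.1.1 repeats this. Under Protocol 6.3, patients unresolved at 60 days have the stent removed and move to treatment outside the protocol, though their outcome is still followed. SAP 4.2 makes the treated cohort primary.

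**The concern.** Time to resolution is incomplete for every patient who does not resolve while under study treatment. If the general rule is applied to the recorded times, the summary is conditional on having resolved. The slowest patients and those who never resolve are left out, so the figure can only move towards shorter times.

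The endpoint carries some weight. Protocol section 1 offers faster resolution as a possible advantage of large-diameter lumen-apposing stents. SAP section 2 allows the analyses to be used in presentations and manuscripts. SAP 5.2 allows informal interim analyses for abstracts, when more patients may still be unresolved. Two analysts working from the present text could also report materially different times from the same data.

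**Working it through.** **Plan figure reproduced first.** The documents give no figure for time to resolution. The nearest stated figure is the plastic-stent resolution rate behind the 67% threshold. A DerSimonian-Laird random-effects analysis on the logit scale, over the seven x/N pairs of SAP Table 1 (302/448 in total), gives 67.0% (60.0%, 73.4%), which matches.

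**Inputs from the documents.** N = 40 (SAP 3.3). Resolution by day 60 is p = 67% (threshold, SAP 3.3.1), 70% (expected) or 76.7% (original IDE, 23/30). The stent period ends at day 60 (Protocol 6.3). A value of 90% was added as an optimistic assumption.

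**Patients without a time by day 60:** 40(1 − p).
- 67%: 40 × 0.33 = 13.2
- 70%: 40 × 0.30 = 12.0
- 76.7%: 40 × 0.233 = 9.3

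**Assumed time distribution.** The documents give none. Take F(t) = 1 − exp[−(t/s)^k], with s = 60/[−ln(1 − p)]^(1/k) so that F(60) = p. Assume no censoring or competing event before day 60.
- All-patient median: s(ln 2)^(1/k)
- Resolver-only median, where F = p/2: s[−ln(1 − p/2)]^(1/k)
- All-patient mean restricted to 60 days (unresolved patients counted as 60): R
- Resolver-only mean: [R − 60(1 − p)]/p

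**Worked case, p = 0.70, k = 1.** The hazard is −ln(0.30)/60 = 0.02007 per day. The all-patient median is 0.6931/0.02007 = 34.5 days. The resolver-only median is −ln(0.65)/0.02007 = 21.5 days. R = 0.70/0.02007 = 34.9 days, and the resolver-only mean is (34.9 − 18)/0.70 = 24.1 days.

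**Other shapes and rates (days):**

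| Resolved by day 60 | k | Median, resolvers | Median, all | Gap | Mean, resolvers | Restricted mean, all | Gap |
|---|---|---|---|---|---|---|---|
| 67% | 0.7 | 14.4 | 30.7 | 16.3 | 19.2 | 32.7 | 13.5 |
| 67% | 1 | 22.1 | 37.5 | 15.4 | 24.6 | 36.3 | 11.7 |
| 67% | 2.5 | 40.2 | 49.7 | 9.5 | 38.8 | 45.8 | 7.0 |
| 70% | 0.7 | 13.8 | 27.3 | 13.5 | 18.8 | 31.1 | 12.3 |
| 70% | 1 | 21.5 | 34.5 | 13.0 | 24.1 | 34.9 | 10.8 |
| 70% | 2.5 | 39.8 | 48.1 | 8.3 | 38.5 | 45.0 | 6.5 |
| 76.7% | 0.7 | 12.4 | 20.8 | 8.4 | 17.6 | 27.5 | 9.9 |
| 76.7% | 1 | 19.9 | 28.5 | 8.6 | 23.0 | 31.6 | 8.6 |
| 76.7% | 2.5 | 38.6 | 44.6 | 6.0 | 37.6 | 42.8 | 5.2 |
| 90% | 0.7 | 8.7 | 10.8 | 2.1 | 14.2 | 18.8 | 4.6 |
| 90% | 1 | 15.6 | 18.1 | 2.5 | 19.4 | 23.5 | 4.1 |
| 90% | 2.5 | 35.0 | 37.1 | 2.1 | 34.7 | 37.3 | 2.6 |

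Shape 1.5 falls inside these ranges. Uniform times at 70% give medians of 30 against 42.9 days and means of 30 against 39.0.

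**Scan rounding.** Resolution is seen only at a scan, so recorded times run late. With k = 1, p = 0.70 and assumed 14-day scans, the resolver-only mean rises from 24.1 to 30.2 days, nearer the 34.9 for all patients. The medians become 28 (resolvers) and 42 (all), so that gap remains.

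**The case against.** A reader might infer that the SAP restricts item 6 to resolvers. It does not: no sentence says so, and the treated cohort is primary. A median over all treated patients is possible under SAP 4.1 if unresolved patients are ranked last, and it is defined whenever more than half resolve. This stands. The defect is a missing method whose likely default is biased; the plan does not state a biased analysis. The mean has no such escape.

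A reader might also infer that about 30% of patients can never have a time. The documents leave this open. Item 6 carries no 60-day limit, outcomes are followed after stent removal, and item 5 counts resolution up to 6 months later. On the other side, the definition requires endoscopic drainage, and imaging at the 6-month visit is only as needed (Protocol 6.1). What can be said is that these patients have no time by day 60, and that no rule covers later resolution.

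A third tempting inference is that the device would be presented too favourably overall. SAP 3.1.2 reports the resolved proportion over all implanted patients with an exact 95% interval, so non-resolution is visible. A resolver-only time, labelled and read beside that proportion, is a fair description. The harm is limited to an unlabelled time quoted by itself.

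Finally, the endpoint is one of eleven additional ones, with no success criterion and no hypothesis test. That limits the importance of the point, but a descriptive estimate should still describe the treated patients.

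**Conclusion.** The point holds as an unspecified analysis with a predictable bias. The direction follows from conditioning on resolution and does not depend on the distribution assumed. The size does. Over 67% to 76.7% resolved and Weibull shapes 0.7 to 2.5, the median is understated by about 6 to 16 days and the mean by about 5 to 14. At the expected 70% the ranges are about 8 to 14 and 6.5 to 12 days. If 90% resolve, they shrink to 2 to 3 and 3 to 5 days. Scan-visit rounding offsets part of the bias in the mean. No single value should be quoted as the expected bias, because the documents give no time distribution. Neither primary endpoint and neither success criterion is affected.

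**What to change.** Add the following to SAP 5.1 item 6:
- **Estimator and population:** cumulative incidence of resolution (Aalen-Johansen) in all treated patients, from first AXIOS stent placement to the first CT or MRI showing 3 cm or less.
- **Competing events:** death, and a switch to drainage or treatment outside the protocol, including after stent removal without resolution. Such patients should not also be censored at removal.
- **Censoring:** only withdrawal or loss to follow-up, at the last scan.
- **Indeterminate cases** (plastic stent at a new site): handled consistently with the primary endpoint, for example by treating that stent as a competing event.
- **Window:** state that item 6 covers resolution up to day 60 or stent removal, leaving later resolution to item 5.
- **Reporting:** day-30 and day-60 cumulative incidence with 95% confidence intervals and, if reached, the time at which 50% have resolved. Label any resolver-only mean or median as such.

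The cost is a paragraph in the SAP and one standard procedure. No new data are needed, because Protocol 6.3 already calls for imaging until the collection is 3 cm or less. The estimate is descriptive, so it fits the SAP's statement that no hypothesis testing will be done.

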5.2 Interim Analyses

No formal interim analyses are planned for the purpose of stopping the study early. Informal interim analysis may be conducted for the purpose of submissions of abstracts to major professional meetings.

5.3 Subgroup Analyses

No subgroup analysis is planned.

5.4 Justification of Pooling

The analyses will be performed using data pooled across institutions. An assessment of the poolability of subjects across sites for the primary effectiveness and safety endpoints will be made by fitting logistic regression models with site as a factor and the primary effectiveness and safety endpoints as outcomes. Certain baseline variables may also be explored for pooling.

If the P value for the site is ≥ 0.05 , it will be concluded that the endpoint is not different across sites, and the data can be pooled. If the P value for site from the logistic model is < 0.05 , site differences will be explored.

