As in the original IDE, #G130264, there is no formal statistical hypothesis for this study. The proportion of AXIOS patients with AXIOS™ stent related or WON drainage procedure related serious adverse events in the original IDE is 10.0% (3/30) [95% CI (2.1%, 26.5%)] patients. A similar rate of AXIOS™ stent related or WON drainage procedure related serious adverse events is expected in this study. This event rate is within the range of reported stent related or WON drainage procedure related serious adverse event rates in several recent publications [3-5, 10] representing 306 patients for which a random effects meta-analysis yields a mid-point related SAE rate of 16.7% [95% CI (10.1%, 26.3%)] for WON drainage with plastic stents (see Table 7.2 and Table 7.3 (categorized events from Table 7.2)), an established WON drainage method as described in the ASGE guidelines on treatment of pancreatic fluid collections [9].

**Table 7.2 Plastic Stent-related or WON Drainage-procedure related Serious Adverse Events Rates from Recent Publications [3-5, 10]**

Study	% Related SAEs (x/N)	95% Confidence Interval
Papachristou (2007)	20.8% (11/53)	(10.8%, 34.1%)
Schmidt (2015)	12.3% (10/81)	(6.1%, 21.5%)
Smoczynski (2015)	25.9% (29/112)	(18.1%, 35.0%)
Varadarajulu (2011)	8.3% (5/60)	(2.8%, 18.4%)
Random-Effect Meta-Analysis	16.7%	(10.1%, 26.3%)

**Table 7.3 Categorized Plastic Stent-related or WON Drainage-procedure related Serious Adverse Events Rates from Recent Publications [3-5, 10]**

SAE	% (x/N)
Bleeding	11.1% (34/306)
Perforation	2.6% (8/306) [5 GI; 2 Collections; 1 Undefined]
Pneumoperitoneum	1.3% (4/306)
Sepsis	0.7% (2/306)*
Stent migration	1.0% (3/306)
Multiple organ failure	1.0% (3/306)
Other - loss of access to the collection (due to hypertension)	0.3% (1/306)

\*Note: 1 patient with septic shock also had multiple organ failure (death)

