1. PROTOCOL SUMMARY

Objective(s)	To demonstrate safety and effectiveness of lumen-apposing metal stents for resolution of walled off pancreatic necrosis (WONs) in patients with WONs with solid component >30%
Test Device	AXIOS™ Stent and Electrocautery Enhanced Delivery System
Control Device	None
Study Design	Prospective, single arm, multi-center trial
Planned Number of Subjects	40
Planned Number of Investigational Sites	Up to 6 centers
Primary Endpoints	
Primary Effectiveness Endpoint:
 
Resolution of WON with endoscopic drainage defined as radiographic decrease of WON size to ≤ 3cm evaluated by CT scan or MRI
 
Primary Safety Endpoint:
 
AXIOS™ stent related or WON drainage procedure related serious adverse events

Additional Endpoints	
 Reduction of WON-related clinical symptoms. Note: WON-related symptoms as defined in Inclusion Criteria #4 in the protocol Technical AXIOS™ stent placement success, defined as placement in desired location using endoscopic/EUS techniques per standard of practice. Technical AXIOS™ stent removal success, defined as ability to remove the AXIOS™ stent using an endoscopic snare or forceps or graspers without AXIOS™ stent removal related serious adverse events. Drainage procedural time: Time elapsed between initial puncture of the WON with electrocautery to endoscope retrieval. Resolution of WON with or without necrosectomy by 6 months post AXIOS™ stent removal. Time to WON resolution using same definition as for primary endpoint, namely:

	
 • Resolution of WON with endoscopic drainage defined as radiographic decrease of WON size to ≤ 3cm evaluated by CT scan or MRI 
7. Recurrence of WON after initial resolution and up to 6 months post AXIOS™ stent removal.
 
8. Stent lumen patency, evaluated via imaging or direct visual inspection with endoscope, and defined as one or both of the following:
 
 • Drainage through AXIOS™ stent visualized from the stomach or bowel, and/or • Visual confirmation of AXIOS™ stent lumen patency 
9. Fluoroscopy (time) per endoscopic procedure.
 
10. Incidence of new organ failure from drainage procedure to WON resolution.
 
11. Change in Quality of Life score (SF-12 questionnaire) from baseline to stent removal and end of study

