3.3 Sample Size and Success Criteria

The WON resolution rates and related SAE rates reported in the above provided study references are similar to those reported for WON drainage using plastic stents in a recent systematic review and meta-analysis comparing plastic stents to metal stents, including lumen-apposing metal stents (LAMS) for the management of WONs [10]. Appendix I in Section 21 of the protocol provides a few key points from this systematic review.

Although reported effectiveness and safety event rates from different sources appear similar, 95% confidence intervals are fairly wide, mostly due to small sample sizes and heterogeneity in WONs and in detailed procedural WON drainage steps. Therefore we chose to increase the sample size of the present study to be slightly larger than in the original IDE study #G130264, which was 30 patients.

We will conduct the present study in 40 patients.

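### The poolability rule names no test and makes no provision for sites without events; if the Wald P value is used, it can declare sites not different when every SAE is at one site

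*SAP*

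**What the plan says.** SAP 5.4 (Justification of Pooling) assesses poolability by "fitting logistic regression models with site as a factor and the primary effectiveness and safety endpoints as outcomes". The decision rule is "If the P value for the site is ≥ 0.05", then "it will be concluded that the endpoint is not different across sites, and the data can be pooled". A P value below 0.05 leads only to exploration of site differences.

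Protocol 7.4 applies the same rule to two factors: "fitting logistic regression models with site (double pigtail plastic stent) as a factor and the primary effectiveness and safety endpoints as outcomes". SAP 5.4 has the site check only.

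The data available to the check are limited. SAP 3.3 says "We will conduct the present study in 40 patients". SAP 1 gives the number of sites as "Up to 6 centers", and SAP 4.4 says "There will be no limit to the number of subjects enrolled at each investigative site". On safety, Protocol 7.2 reports 3/30 (10.0%) in IDE #G130264 and adds "A similar rate of AXIOS™ stent related or WON drainage procedure related serious adverse events is expected in this study".

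Neither document says whether the P value comes from a Wald, likelihood-ratio, score or exact test. Neither says how a site or stent group with no events, or with only events, is handled. SAP 7.1 names SAS 9.2 or later without a procedure or option.

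**The concern.** With few events spread over several sites, some sites will have none. In an ordinary logistic model with site as a factor, the coefficients for those sites then have no finite maximum likelihood estimate (quasi-complete separation). As the fit iterates, the estimates drift outwards and their standard errors grow much faster. A Wald statistic built from them shrinks towards zero, and its P value rises towards 1 however uneven the sites are.

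A rule that concludes no difference at 0.05 or more would then pass the data in just the case it should catch. This is not the same as low power, because other tests of the same factor on the same data can detect the difference. No subgroup analysis is planned (SAP 5.3) and neither document commits to by-site rates, so this P value is the only planned look at site differences in the primary endpoints.

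**Working it through.** **Inputs.** From the documents: 40 treated patients; up to 6 sites; no cap per site; related-SAE rate in IDE #G130264 of 3/30; safety success limit 17.5%; expected resolution rate 70%. Assumed, because the documents do not give them: how patients split across sites (7/7/7/7/6/6 as the base case, others as the range) and how many receive a plastic stent.

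**1. The plan's own figure.** The Clopper-Pearson limits for 3/30 are the 2.5% point of Beta(3, 28) and the 97.5% point of Beta(4, 27), that is 2.1% and 26.5%. These match Protocol 7.2. The expected count is 0.10 × 40 = 4 patients.

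**2. Separation.** Four patients with an SAE can occupy at most 4 of 6 sites, so at least 2 have none. If all six sites enrol and the count is 4, separation is certain. With a random count at rate r, the chance of at least one all-or-none site is 1 − Π[1 − rⁿ − (1 − r)ⁿ], taken over site sizes n. For r = 0.10 a 7-patient site contributes 1 − 0.10⁷ − 0.90⁷ = 0.5217 and a 6-patient site 0.4686, so the chance is 1 − 0.5217⁴ × 0.4686² = 0.984.

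| Layout | SAE 10% | SAE 17.5% | Resolution 70% |
|---|---|---|---|
| Six sites, 7/7/7/7/6/6 | 98% | 86% | 45% |
| Six sites, 15/9/6/4/3/3 | 99% | 95% | 75% |
| Four sites of 10 | 82% | 47% | 11% |
| Three sites, 14/13/13 | 57% | 21% | 3% |

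**3. All 4 SAEs at one 7-patient site (4/7 v 0/33), base-case layout.**
- Wald, 5 df, Newton-Raphson from zero: chi-square 1.36 after 6 iterations (P = 0.93), 0.30 after 8 (P = 0.998), 0.01 after 12 (P = 1.000).
- Likelihood ratio: the null log-likelihood is 4 ln(0.1) + 36 ln(0.9) = −13.003. With site it is 4 ln(4/7) + 3 ln(3/7) = −4.780, because the zero-event sites contribute 0. The statistic is 2 × (13.003 − 4.780) = 16.45 on 5 df, P = 0.0057.
- Exact (Fisher-Freeman-Halton): the tables at least as improbable are those with all four events at a single site, (4 × 35 + 2 × 15)/91,390 = 170/91,390 = 0.0019.

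**4. Other splits of events, same layout.** For 5/7 v 0/33, Wald P runs from 0.90 to 1.00 over 6 to 12 iterations; likelihood-ratio P is 0.0006 and exact P 0.00015. With 6/7 at one site and 1/7 at another (7/40 = 17.5%, which still meets the safety criterion), Wald P is 0.26 to 0.36, likelihood-ratio P 0.0001 and exact P 0.00005.

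**5. Repeated sampling.** With true rates of 57% at one 7-patient site and 0% elsewhere, the Wald test rejected in 0 of 3,000 simulated trials and the likelihood-ratio test in 87%.

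**6. Plastic-stent check, assumed 4/10 v 0/30.** Wald P is 0.31, 0.63 and 0.92 after 6, 8 and 12 iterations. Likelihood-ratio P is 0.0004 and Fisher P 0.0023.

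**7. Limits of the alternatives.** All 4 SAEs at the largest of six sites:

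| Patients at that site | Likelihood-ratio P | Exact P |
|---|---|---|
| 10 | 0.028 | 0.040 |
| 12 | 0.057 | 0.17 |
| 15 | 0.13 | 0.37 |
| 20 | 0.31 | 0.70 |

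Under no true site difference, the simulated likelihood-ratio test rejected in 2.3% to 2.6% of trials at a 10% SAE rate, 6.0% to 6.8% at 17.5%, and 8.8% to 8.9% for resolution at 70%. It is therefore somewhat liberal at the higher rates.

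**The case against.** A reader might infer that the model cannot be estimated and that its P value must therefore be near 1. The documents do not support that. Infinite coefficients break the Wald test, but the likelihood still has a finite limit, and the likelihood-ratio test from the same ordinary logistic model gives 0.006 in step 3. The plan does not say that Wald is the test; that would be an assumption about software practice. This objection stands, and it limits the point to a conditional failure plus a gap in specification.

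A reader might also infer that a safety problem would be cleared. That goes too far. SAP 5.4 pools across institutions from the outset, a P below 0.05 only triggers exploration, the success criteria are observed pooled rates (SAP 3.3), and SAE reporting under Protocol 15 runs independently of this check.

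Three further objections hold in part. The certainty of separation depends on six sites enrolling, and the chance falls to 57% with three. The plastic-stent Wald P depends on when the fit stops, so near 1 is not a fair description of it. And low power remains: when the affected site is large, the likelihood-ratio and exact tests miss the clustering too.

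What survives is that one dataset can give pool or explore depending on a test chosen after the data are seen.

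**Conclusion.** The point holds in conditional form. SAP 5.4 and Protocol 7.4 leave the test and the handling of zero-event sites unspecified, in a study where separation is certain with 4 SAEs over six enrolling sites and likely at the expected rate with fewer (82% with four sites, 57% with three). If the Wald P value is used, it is 0.998 or higher after 8 iterations with every SAE at one of six near-equal sites, against 0.006 (likelihood ratio) and 0.002 (exact). The rule would then declare the sites not different on data that a valid test flags.

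The size of the contrast rests on the assumed site split, on the affected site being small (up to about 10 patients), and on the Wald test being the one reported. The effect is on the poolability conclusion only; the primary estimates, their confidence intervals and the success criteria are unaffected. It should be corrected, but it does not threaten the main result.

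**What to change.** In SAP 5.4 (site) and Protocol 7.4 (site and plastic-stent group), replace the unspecified logistic P value with a named test. A Fisher-Freeman-Halton exact test or exact logistic regression is the simplest choice. A likelihood-ratio test, or Firth penalised likelihood with a profile-likelihood test, is acceptable if a model is wanted.

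Add two sentences. First, report x/n with a Clopper-Pearson 95% interval by site and by plastic-stent group for both primary endpoints, whatever the P value. Second, do not take a P value of 0.05 or more as evidence that sites or groups are the same.

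The cost is a few lines of text and a SAS option (EXACT in PROC FREQ, or the exact or Firth options for logistic regression); no new data are needed. The drawback is that an exact test is conservative and can miss clustering at a large site (P = 0.37 with all 4 SAEs at a 15-patient site), so the by-site table has to accompany it.
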